Official Title of the study:

Fibrinolysis Compared to Thoracoscopy for Pleural Infection

NCT number:

NCT03468933

Date of the document:

July 1, 2017

Statistical Analysis

We believe that a difference of 2 days in the length of the postintervention hospital stay between the two treatment arms would be clinically important. This rationale is based on a previous randomized study that compared VATS and streptokinase therapy in empyema (1). In that study, the number of chest tube days after VATS was 5.8 ± 1.1 days, as compared with 9.8 ± 1.3 days in the streptokinase group. Furthermore, a case series from MT trials reported an average postoperative stay of 7–8 days (2-5), as compared with an average of 10–13 days in IPFT trials (6,7). According to a two-sided type I error of 0.05 and 80% power, the sample size was 16 patients in each group.

All analyses were performed using GraphPad Prism (version 7.0; GraphPad Software). Descriptive statistics were used to summarize the patients' characteristics. The t test was used to examine differences between groups with parametric data and the Mann-Whitney U test was used for nonparametric data. Fisher's exact test was used for categorical variables. A P value of <0.05 was considered statistically significant.

- 2-BrutscheMH, Tassi GF,Gyo" rik S,Go" keimenM, Renard C,MarchettiGP, et al. Treatment of sonographically stratified multiloculated thoracic empyema by medical thoracoscopy. Chest 2005;128:3303–3309.
- 4-Sole`r M, Wyser C, Bolliger CT, Perruchoud AP. Treatment of early parapneumonic empyema by "medical" thoracoscopy. Schweiz Med Wochenschr 1997;127:1748–1753.

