A chest tube (14-French Seldinger or less) under ultrasonography guidance will be inserted into the most dependent area of the pleural effusion or into the largest loculation in patients with multiloculated effusions. The dose of DNase (Pulmozyme, Genentech, USA) is 5 mg and the dose of tPA (Actilyse, Genentech, USA) is 10 mg, each in 50 ml of 0.9% NaCl. tPA and DNase will not be mixed together in one syringe. Concurrent tPA and DNase will be administered intrapleurally through the chest tube followed by 60 ml saline flush. The tube will then be clamped for 120 minutes before the chest tube will be opened to -20 cmH₂O of wall suction. Therapy will be given twice daily for a maximum of 6 doses. A chest CT without contrast will be performed and if there was no evidence of significant pleural effusion²⁸ and chest tube drainage is <75 ml/day, the catheter will be removed.

Study Outcome

Primary outcome measure:

- Duration of hospital stay after intervention

Secondary outcome measures:

- Total length of hospital stay
- Failure rate of assigned treatment (persistent fever, leukocytosis evidence of loculation 48 hours post intervention) necessitating intervention defined as any of the following:
 - 1-Surgical intervention (VATS, open thoracotomy) in the medical thoracoscopy or fibrinolytic therapy arm
 - 2-Need of additional chest tube and/or fibrinolytic therapy in the medical thoracoscopy arm due to clinical non-responsiveness
 - 3-Need of additional chest tube in the fibrinolytic therapy arm due to clinical non-responsiveness
- Adverse events
 - Pleural bleeding defined as drop in serum hematocrit requiring blood transfusion or causing hemodynamic instability
 - Significant pain requiring escalation of analgesia
- In hospital and 30 day mortality

[figure not shown]

Figure 3. Proposed Study Protocol

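### Does the missing standard deviation for hospital stay undermine the stated 80% power with 16 patients per group?

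*SAP*

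**What the plan says.** The primary outcome in the Protocol (Study Outcome) is "Duration of hospital stay after intervention". The SAP (Statistical Analysis) sets the target: "We believe that a difference of 2 days in the length of the postintervention hospital stay" between arms is regarded as clinically important.

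Two pieces of background follow. The first is a randomized comparison of VATS and streptokinase, cited as reference (1), in which "the number of chest tube days after VATS was 5.8 ± 1.1 days, as compared with 9.8 ± 1.3 days in the streptokinase group". The second is a set of average hospital stays, 7–8 days for medical thoracoscopy and 10–13 days for intrapleural fibrinolysis, given without SDs.

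The size is then stated in one sentence: "According to a two-sided type I error of 0.05 and 80% power, the sample size was 16 patients in each group". No SD for hospital stay, allowance for dropout or inflation for a rank test is given. The Protocol has no sample-size text.

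**The concern.** A sample size for comparing two means needs a difference, an error rate, a power and an SD. The SAP gives the first three for hospital stay and omits the fourth. A reader who takes the only printed SDs gets less than half the stated size, so the calculation seems not to hang together. Those SDs also describe a different endpoint under treatments that neither arm of this trial receives. The trail stops at reference (1) as well: its listed title is a single-centre experience with tPA and DNase, not a randomized VATS versus streptokinase study.

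What would be at stake is how a non-significant result is read. If stay varies much more than the planners assumed, the trial has well under 80% power for 2 days, and a null finding could be taken as stronger evidence against a 2-day difference than it is.

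**Working it through.** **Inputs.** From the SAP: difference δ = 2 days, two-sided α = 0.05, power 80%, n = 16 per group, and chest-tube SDs of 1.1 and 1.3 days. The SD of hospital stay is not given, so every value used for it below is an assumption.

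**Step 1: reproduce the stated size.** The normal-approximation formula per group is

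n = 2 (z₀.₉₇₅ + z₀.₈₀)² SD² / δ², with (1.960 + 0.8416)² = 7.849.

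With SD = 2: n = 2 × 7.849 × 4 / 4 = 15.7, rounded up to **16**, the stated figure. Power at 16 is then 80.7% by the same approximation.

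**Step 2: solve for the SD implied by 16.** SD = √(16 × 4 / (2 × 7.849)) = √4.077 = 2.02 days. The exact t-test calculation gives 1.95 days. Both are about 2.

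**Step 3: try the printed SDs.** The pooled value is √((1.1² + 1.3²)/2) = √1.45 = 1.204. Then n = 2 × 7.849 × 1.45 / 4 = 5.7, or 6 per group; the t test needs 7. Across SDs of 1.1 to 1.3 the t test needs 6 to 8, and inflating for a Mann-Whitney test brings this to at most 10. The printed SDs do not yield 16 with a two-sided test at 80% power.

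**Step 4: sensitivity to the SD, for a 2-day difference.**

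| SD (days) | n per group, normal | n per group, t test | Power at 16 per group, t test |
|---|---|---|---|
| 1.204 | 6 | 7 | 99.5% |
| 1.95 | 15 | 16 | 80.2% |
| 2 | 16 | 17 | 78.1% |
| 2.5 | 25 | 26 | 59.1% |
| 3 | 36 | 37 | 44.6% |
| 4 | 63 | 64 | 27.8% |
| 5 | 99 | 100 | 19.5% |

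At SD 2 the gap between the formulas is one patient per group, or about 2 percentage points of power below the nominal 80%.

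**Step 5: is an SD of 2 out of line with the documents?** Against mean stays of 7 to 13 days it is a coefficient of variation of 2/13 = 15% to 2/7 = 29%. The only variability printed has coefficients of 1.1/5.8 = 19% and 1.3/9.8 = 13%. Applied to stays of 7 to 13 days, these span roughly 0.13 × 7 = 0.9 to 0.19 × 13 = 2.5 days. This is a different outcome, so the comparison proves nothing about stay, but an SD of 2 lies inside that range.

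**The case for a change.** The strongest case for acting is that the 80% is the only justification for the trial's size and cannot be checked. It rests on a value the reader must guess, and on a small one: an SD of 2 days is tight for hospital stay, and the SAP itself provides for nonparametric data. If the true SD were 4 days, the 95% confidence interval for the difference would have a half-width of about 2.9 days (2.042 × 4 × √(2/16)), and a null result could not exclude a 2-day benefit. Writing down the SD and correcting the reference would cost nothing.

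Part of this stands. The SD is undisclosed, the power cannot be verified from the documents alone, and reference (1) does not match the study described. The rest is weaker. No figure in either document supports an SD of 3, 4 or 5 days for stay. The rule on t test and Mann-Whitney is a general one and does not say that stay is skewed. Neither document says a non-significant result will be taken as proof of no difference, and no equivalence or non-inferiority claim is made. The quoted average stays differ by 2 days (8 versus 10) to 6 days (7 versus 13), so the 2-day target is the bottom of the cited range. For a 4-day difference, t-test power at 16 per group is 78% even with an SD of 4, because the ratio of difference to SD is the same as 2 days at SD 2.

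**Conclusion.** No change to the plan is needed. The stated size is what the usual formula gives for 2 days, two-sided 5%, 80% power and a round SD of 2 days. That this SD was the one used is an inference, and it assumes that 2 days, the only target the SAP names, was the design difference. The comparison with 6 to 8 per group tests a calculation the SAP never claims, since it presents the chest-tube data as grounds for the 2-day difference. Had those SDs been the planning values, 16 per group would have 98.8% power or more, the opposite of a shortfall.

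What remains is an unprinted planning input and a clerical mismatch in reference (1). Supplying the SD would alter neither the number randomized, the test nor the primary estimate. The confidence interval for the difference in stay depends on the variability observed in the trial, not on the planning SD, so it will show how far a 2-day difference can be excluded. The documents do not show that 16 per group is too few, and they do not show that it is enough if stay varies by much more than 2 days.

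### Must the SAP name the test for post-intervention stay and plan a confidence interval to read against its 2-day difference?

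*SAP*

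**What the plan says.** The protocol's Study Outcome section names one primary outcome, "Duration of hospital stay after intervention". The SAP's Statistical Analysis section holds that "a difference of 2 days in the length of the postintervention hospital stay between the two treatment arms would be clinically important" and sizes the trial on it: "According to a two-sided type I error of 0.05 and 80% power, the sample size was 16 patients in each group".

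The analysis paragraph that follows is generic. For continuous variables it says "The t test was used to examine differences between groups with parametric data and the Mann-Whitney U test was used for nonparametric data", and for all results "A P value of <0.05 was considered statistically significant". It does not assign a test to post-intervention stay, say how data are classed as parametric, or plan a mean or median difference with a confidence interval. Descriptive statistics are mentioned only for patient characteristics. The protocol contains no analysis text that fills these gaps.

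**The concern.** Two things look wrong.

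- **The test is left open.** With two tests listed and no criterion, the choice for the primary outcome could be made after seeing which one reaches significance.
- **The 2 days drops out of the analysis.** The trial is built around a difference in days, yet the only stated criterion is a P value. A result could be significant with an observed difference below 2 days and be read as an important benefit. It could also be non-significant with 2 days still plausible and be read as showing no benefit. With 16 patients per arm, both are possible.

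If this were serious, the type I error would be materially above 5%, or the trial's main conclusion would depend on something the plan withholds.

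**Working it through.** **Inputs from the SAP's Statistical Analysis section:** 16 per arm, difference 2 days, two-sided 0.05, 80% power. No SD for hospital stay is given. The only dispersions printed are ±1.1 and ±1.3, unlabelled and for chest tube days in a cited study.

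**1. The plan's own figure.** n per arm = 2(z₀.₉₇₅ + z₀.₈₀)² × SD² / δ². The pooled printed value is √((1.1² + 1.3²)/2) = 1.20, so n = 2 × 2.802² × 1.45 / 4 = 5.7, rounded up to 6 (7 by noncentral t). This does not reproduce 16, but chest tube days are not hospital stay, so it does not show that 16 is wrong. Solving backwards, n = 16 implies an SD of 2.02 days (normal approximation) or 1.95 days (noncentral t, 30 df). I use 1.95 as the plan's implied SD, and vary it.

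**2. Width of the interval.** Half-width = t₀.₉₇₅,₃₀ × SD × √(2/16) = 2.042 × 1.954 × 0.354 = 1.41 days.

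| SD (days) | 95% half-width (days) |
|---|---|
| 1.2 (printed, chest tube days) | 0.87 |
| 1.95 (implied by n = 16) | 1.41 |
| 3 (assumed) | 2.17 |
| 4 (assumed) | 2.89 |

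At SD 1.95, P<0.05 is reached at an observed difference of 1.41 days. Two days lies inside the interval for observed differences from 2 − 1.41 = 0.59 to 2 + 1.41 = 3.41.

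**3. Is the 1.4 days peculiar to this plan?** No. 1.41/2 = 0.705. In large samples the ratio is 1.960/(1.960 + 0.842) = 0.70. Every two-sided 5% trial sized at 80% power becomes significant at about 70% of its design difference. Printing an interval shows this but does not remove it.

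**4. How often does P alone leave 2 days unsettled?** Take normal data with SD 1.95, so the standard error is 1.954 × 0.354 = 0.69.

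- *True difference 0.* A non-significant trial has an interval reaching 2 days if the observed difference lies between 0.59 and 1.41, that is 0.85 to 2.04 standard errors. The probability is (0.197 − 0.021)/0.959 = 18%. Simulation with the SD estimated in each trial gives 19%. At SD 3 and 4 it gives about 55% and 74%.
- *True difference 4* (the chest-tube-day gap the SAP cites, 9.8 − 5.8). A significant trial has a lower limit below 2 if the observed difference is under 3.41: P(Z < −0.85) = 20%.
- *True difference 2.* With assumed lognormal stays, means 7 and 9 and CV 0.3–0.7, 92–96% of non-significant t tests have an interval reaching 2 days, and 92–97% of significant ones have a lower limit below 2. These look alarming, but a 95% interval covers its true value about 95% of the time, and here the true value is 2. They mostly restate coverage.

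**5. What does the open choice of test cost?** Simulation: 16 per arm, assumed lognormal stays, CV 0.3, 0.5 and 0.7, 20,000 trials per setting (simulation error about 0.15 points at a 5% rate).

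| Quantity | Result |
|---|---|
| Type I error, test chosen by Shapiro-Wilk pre-test (mean 8 in both arms) | 5.1–5.6% |
| Type I error, smaller of the two P values | 5.7–6.3% |
| Tests disagree on significance, no true difference | 2–3% |
| Tests disagree on significance, means 7 and 9 | 8–9% |
| Power, t test, CV 0.3 / 0.5 / 0.7 | 63 / 28 / 16% |
| Power, Mann-Whitney, CV 0.3 / 0.5 / 0.7 | 62 / 28 / 18% |

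If stay is normal with an assumed SD of 2, power is 78% for the t test and 75% for Mann-Whitney. Neither choice gains or loses more than about 3 points.

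**The case for a change.** The best case for a change is that it would cost a sentence, and nothing in the plan binds the analyst without it. When the arms truly differ by 2 days, the two tests disagree on significance in 8–9% of the simulated trials, so the choice can decide how the result is described. The matching estimates also differ. Under the same lognormal assumptions, a 2-day mean difference corresponds to a Hodges-Lehmann shift of 1.88, 1.69 or 1.49 days at CV 0.3, 0.5 or 0.7. If the SD of stay is nearer 3 or 4 than 1.95, a non-significant result says little about 2 days unless an interval is shown.

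Much of this stands. The plan provides no comparison of the result with 2 days, and a report that gave only a P value would be poor. But the objection concerns good reporting, not an analysis that goes wrong. The SAP limits the choice to two standard tests, and either would be acceptable as primary. Even the worst use of the freedom moves the type I error by about one point. The t test's difference and interval come from the same means, SDs and counts as its P value, so they need no new decision or data. The SAP also keeps its two ideas apart: 2 days is its standard of clinical importance, and P<0.05 its standard of statistical significance. It nowhere equates them.

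**Conclusion.** No change to the plan is needed. The SAP leaves out detail that analysts fill sensibly: one of two standard tests for stay, reported with its difference in days and a 95% interval. Followed as written, the plan gives a valid two-sample comparison with type I error of about 5.1–5.6% under a normality pre-test. Naming either listed test would move power by at most about 3 points. The 1.4-day significance threshold is a property of sizing at 80% power, and 2 days is a design target that calls for no formal test.

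The interval widths rest on an SD of 1.95 days back-solved from the sample size, since none is given for stay. The error rates and disagreement rates rest on assumed lognormal stays with CV 0.3–0.7. A larger SD makes the interval more useful to readers, but it does not make either test invalid.
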